Grade 4 pulmonary embolism		See table 8. If binimetinib is permanently discontinued, encorafenib should be discontinued.	Binimetinib should be permanently discontinued.
Interstitial lung disease (ILD)/Pneumonitis		Encorafenib	Binimetinib
Grade 2		See table 8. If a patient temporarily interrupts (withheld) treatment with binimetinib, the patient may continue treatment with encorafenib as monotherapy at a maximum dose of 300 mg QD.	Binimetinib should be withheld for up to 4 weeks.  If improved to Grade 0 or 1, binimetinib should be resumed at reduced dose.  If it is not resolved within 4 weeks, binimetinib should be permanently discontinued.
Grade 3 or 4		See table 8. If binimetinib is permanently discontinued, encorafenib should be discontinued.	Binimetinib should be permanently discontinued.
Diarrhea		Encorafenib	Binimetinib
Grade 1-2	Uncomplicated	See table 8. If a patient temporarily interrupts (withheld) treatment with binimetinib, the patient may continue treatment with encorafenib as monotherapy at a maximum dose of 300 mg QD.	Binimetinib should be withheld for up to 4 weeks.  • If improved to Grade 0 or 1, binimetinib should be resumed at same dose.
	Complicated	Encorafenib should be withheld for up to 4 weeks.  • If improved to Grade 0 or 1, encorafenib should be resumed at same dose.	Binimetinib should be withheld for up to 4 weeks.  • If improved to Grade 0 or 1, binimetinib should be resumed at reduced dose.
Grade 3-4		Encorafenib should be withheld for up to 4 weeks.  • If improved to Grade 0 or 1, encorafenib should be resumed at same dose, if in the judgment of the investigator the toxicity is unrelated to encorafenib, or at one reduced dose.	Binimetinib should be withheld for up to 4 weeks.  • If improved to Grade 0 or 1, binimetinib should be resumed at reduced dose.
Nausea/Vomiting		Encorafenib	Binimetinib

Grade 1-2	Treatment with encorafenib and binimetinib should be maintained at the current dose. Promptly institute antiemetic measures.	
Grade 3	Encorafenib should be withheld for up to 4 weeks.  • If improved to Grade 0 or 1, encorafenib should be resumed at reduced dose.	Binimetinib should be withheld for up to 4 weeks.  • If improved to Grade 0 or 1, binimetinib should be resumed at the same dose if, in the judgment of the investigator, the toxicity is unrelated to binimetinib, or at one reduced dose.
Grade 4	Encorafenib and/or binimetinib should be permanently discontinued.	

Note: Interrupt dose for  $\geq$  grade 3 vomiting or grade 3 nausea only if the vomiting or nausea cannot be controlled with optimal antiemetics (as per local practice).

Rhabdomyolysis/Creatine phosphokinase (CK) increase		Encorafenib	Binimetinib					
Asymptomatic grade 3 CK >5 – 10x ULN		Encorafenib and binimetinib sho ensured that the patient has an ad	buld be maintained and it should be lequate hydration.					
Asymptomatic grade 4	CK >10x ULN	Binimetinib should be withheld until improved to Grade 0 or 1, moreover, an adequate hydration of the patient should be ensured.						
Grade 3 or 4 with renal impairment or muscle symptoms		See table 8. If a patient temporarily interrupts (withheld) treatment with binimetinib, the patient may continue treatment with encorafenib as monotherapy at a maximum dose of 300 mg QD	Binimetinib should be withheld until improved to Grade 0 or 1, moreover, an adequate hydration of the patient should be ensured.  If resolved within 4 weeks, binimetinib should be resumed at reduced dose or permanently discontinued.					
Retinal pigment epithelial detachment (RPED)ª		Encorafenib	Binimetinib					
Grade 2 Symptomatic		See table 8. If a patient temporarily interrupts (withheld) treatment with binimetinib, the patient may continue treatment with encorafenib as monotherapy at a maximum	Binimetinib should be withheld for up to 2 weeks and ophthalmic monitoring should be repeated including visual acuity assessment.  • If improved to Grade 0 or 1,					

		dose of 300 mg QD	binimetinib should be resumed at the same dose.  • If not improved to Grade 0 or 1, binimetinib should be resumed at a lower dose.		
Grade 3	Symptomatic	See table 8. If a patient temporarily interrupts (withheld) treatment with binimetinib, the patient may continue treatment with encorafenib as monotherapy at a maximum dose of 300 mg QD	Binimetinib should be withheld for up to 2 weeks and ophthalmic monitoring should be repeated including visual acuity assessment.  • If improved to Grade 0 or 1, binimetinib should be resumed at same dose.  • If improved to Grade 2, binimetinib should be resumed at a lower dose.  If not improved to Grade 2, binimetinib should be permanently discontinued.		
Grade 4 Symptomatic with reduced visual acuity		See table 8. If binimetinib is permanently discontinued, encorafenib should be discontinued	Binimetinib should be permanently discontinued.		
Retinal vein occ	clusion (RVO)ª	Encorafenib	Binimetinib		
Any grade		See table 8. If binimetinib is permanently discontinued, encorafenib should be discontinued	Binimetinib should be permanently discontinued.		
Uveitis, iritis and/or iridocyclitis a					
	d/or iridocyclitisª	Encorafenib	Binimetinib		
Grade 1 or 2	d/or iridocyclitis a	Initiate specific ocular therapy (e.g  If Grade 1 or 2 uveitis does n encorafenib and binimetinib shoul should be repeated within 2 weeks  If Grade 1 and improves to resumed at the same dose.	topical).  not respond to specific ocular therapy, d be withheld and ophthalmic monitoring		

Grade 4	Encorafenib and binimetinib should be permanently discontinued and an ophthalmologic monitoring should be performed until resolution.				
aNOTE: Any visual acuity impairment baseline	nt at screening should be docum	nented and should be considered as			
Other adverse reactions	Encorafenib	Binimetinib			
Recurrent or intolerable Grade 2 or First occurrence Grade 3	
 
Encorafenib and/or binimetinib should be withheld for up to 4 weeks (see table 8 to adjust encorafenib dose as monotherapy if it was not interrupted).
 
If improved to Grade 0 or 1 or to baseline levels, then, encorafenib and/or binimetinib should be resumed at a reduced dose.
 
If not improved, encorafenib and/or binimetinib should be permanently discontinued.
 
				
Recurrent Grade 3	It should be considered to permanently discontinue encorafenib and binimetinib.				
First occurrence Grade 4	
 
Encorafenib and/or binimetinib should be withheld for up to 4 weeks (see table 8 to adjust encorafenib dose as monotherapy if it was not interrupted too).
 
If improved to Grade 0 or 1 or to baseline levels, then encorafenib and/or binimetinib should be resumed at a reduced dose level.
 
If not improved, encorafenib and binimetinib should be permanently discontinued.
 
Or, encorafenib and/or binimetinib should be permanently discontinued.
 
				
Recurrent Grade 4	Encorafenib and binimetinib should be permanently discontinued.				

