# 7.2. Dose modifications

Patients will be monitored for adverse events at each visit with the NCI CTCAE version 4.03 used for all grading. If a patient develops a toxicity, the dose may be adjusted as outlined in Table 8-9 and Table 10, which include criteria for interruption and re-initiation of encorafenib and binimetinib. All dose modifications should be based on the worst preceding toxicity (CTCAE version 4.03). All dosing interruptions and changes must be recorded on the Dosage Administration Record at eCRF.

Eye disorders should be graded according to CTCAE version 4.03 as described below in Table 3.

Table 3. CTCAE grading for eye disorders

Grade	Description		
1	Asymptomatic or mild symptoms; clinical or diagnostic observations only; intervention not indicated; no change in vision		
2	Moderate; minimal, local or non-invasive intervention indicated; limiting instrumental ADL; best corrected visual acuity 20/40 and better or 3 lines or less decreased vision from known baseline		
3	Severe or medically significant but not immediately sight threatening; limiting self-care ADL; decrease in visual acuity (best corrected visual acuity worse than 20/40 or more than 3 lines of decreased vision from known baseline, up to 20/200)		
4	Sight-threatening consequences; urgent intervention indicated; best corrected visual acuity of 20/200 or worse in the affected eye		
ADL = Activities of Daily Living			

Retinal detachment should be graded according to the CTCAE version 4.03 as described below in Table 4.

Table 4. CTCAE grading for retinal detachment

Grade	Description	
1	-	
2	Exudative and visual acuity 20/40 or better	
3	Rhegmatogenous or exudative detachment; operative intervention indicated; decline in vision (worse than 20/40 but better than 20/200	
4	Blindness (20/200 or worse) in the affected eye	
Definition: A disorder characterized by the separation of the inner retina layers from the underlying pigment epithelium.		

Uveitis should be graded according to the CTCAE version 4.03 as described below in Table 5

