should not be reduced or interrupted for Grade 1 toxicities, but treatment to control symptoms should be provided as appropriate. All AEs should be followed weekly or as clinically appropriate until stabilization or resolution.

If a patient temporarily interrupts treatment with binimetinib, the patient must continue treatment reducing encorafenib at dose of 300 mg QD, if patient was receiving 450 mg QD of encorafenib in combination with binimetinib (see Table 8 for encorafenib dose reductions). However, if a patient discontinues treatment with encorafenib, they must discontinue treatment with binimetinib, complete the end of treatment visit and continue to be followed until disease progression. Please refer to table 10 for dose adjustment recommendations for encorafenib and/or binimetinib induced toxicities.

Table 10. Encorafenib and binimetinib – Recommended dose modifications associated with treatment-related adverse events

Worst toxicity CTCAE v 4.03 Grade (unless otherwise specified)	Dose adjustments of both drugs	
Cutaneous reactions	Encorafenib	Binimetinib
Grade 2	Encorafenib and binimetinib should be maintained.  If rash worsens or does not improve within 2 weeks with treatment, encorafenib and binimetinib should be withheld until being Grade 0 or 1 toxicity. Then:  If it is the first occurrence of Grade 2, both drugs can be resumed at the same dose.  If it is a recurrent Grade 2 toxicity, both drugs should be resumed at a reduced dose.	
Grade 3	
 
Encorafenib and binimetinib should be withheld until improvement to Grade 0 or 1 toxicity. Then:
 
If it is the first occurrence of Grade 3, both drugs can be resumed at the same dose.
 
If it is a recurrent Grade 3 toxicity, both drugs should be resumed at a reduced dose.
 
	
Grade 4	Encorafenib and binimetinib should be permanently discontinued.	
Squamous Cell Carcinoma (SCC), Keratoacanthoma (KA) or any other suspicious skin lesion	Encorafenib	Binimetinib
Grade 3-4	Encorafenib and binimetinib should be maintained at same dose and local treatment of lesion (e.g. new primary melanoma) should be done based upon institutional practice.	
Palmar-plantar erythrodysaesthesia syndrome (PPES)	Encorafenib	Binimetinib

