# 7.2.2. Follow-up for toxicities

Patients whose treatment is interrupted or permanently discontinued due to an adverse event or clinically significant laboratory value, must be followed up at least once a week (or more frequently if required by institutional practices, or if clinically indicated) for 4 weeks, and subsequently at approximately 4-week intervals, until resolution or stabilization of the event, whichever comes first. Appropriate clinical experts such as an Ophthalmologist, cardiologist or dermatologist should be consulted as deemed necessary. Further guidelines and recommendations for the management of specific study drug Combination induced toxicities are provided in table 10.

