# 7.2.2.3. Management of nausea and/or vomiting

Because nausea and vomiting have been reported for encorafenib and binimetinib, it is recommended that patients are educated on the possibility of occurrence of these side effects prior to starting study treatment. Patient education as well as proper management of nausea and/or vomiting at the first sign is important. Clinical judgment and experience of the treating physician should guide the management plan of each patient. Patients experiencing nausea and/or vomiting CTCAE ≥1 will receive antiemetics at the discretion of the treating physician (as per local guideline). It is recommended that patients be provided a prescription for antiemetics and are instructed on the use of antiemetics on the first day of study drug treatment. Prophylactic antiemetics such as dexamethasone 8 mg, prochlorperazine, or metoclopramide may be administered to patients on an "as needed" basis.

Dose interruption/reduction decisions for nausea and/or vomiting should be based on the CTCAE grade of the toxicity and the guidelines provided in table 10.

As a guidance for recommendations on supportive measures for the prevention and/or management of nausea and/or vomiting, the published recommendation from American Society of Clinical Oncology (ASCO) , the European society of Medical Oncology (ESMO) and Multinational Association of supportive Care (MASCC)  can be used.

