#### 9.3.3. Severity assessment

Severity of AEs will be assessed according to the CTCAE which provides a descriptive terminology, which can be utilized, for Adverse Event (AE) reporting. A grading (severity) scale is provided for each AE as follows:

Grades: Grade refers to the severity of the AE. The CTCAE displays Grades 1 through 5 with unique clinical descriptions of severity for each AE based on this guideline:

- Grade 1 Mild; asymptomatic or mild symptoms; clinical or diagnostic observations only; intervention not indicated
- Grade 2 Moderate; minimal, local or non-invasive intervention indicated; limiting age-appropriate instrumental Activities of Daily Living (ADL)\*
- Grade 3 Severe or medically significant but not immediately life-threatening; hospitalization or prolongation of hospitalization indicated; disabling; limiting self-care ADL\*\*
- Grade 4 Life-threatening consequences; urgent intervention indicated
- Grade 5 Death related to AE

\*Instrumental ADL refer to preparing meals, shopping for groceries or clothes, using the telephone, managing money, etc.

\*\*Self-care ADL refer to bathing, dressing and undressing, feeding self, using the toilet, taking medications, and not bedridden.

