# 11.4. Independent Ethical Committee (IEC) or Institutional Review Board (IRB) Review

Prior to commencement of the trial at a given site, this clinical trial protocol will be submitted together with its associated documents to the Central IEC for its favourable opinion, which will be filed in the Investigator Site File. A copy will be filed in the Sponsor Trial Master File.

The IEC will be asked to document the date of the meeting at which the favourable opinion or approval was given and the members and voting members present. Written evidence of favourable opinion or approval that clearly identifies the trial, the clinical trial protocol version and the Subject Information and Informed Consent Form version reviewed should be provided.

Amendments to this clinical trial protocol will also be submitted to the concerned IEC or IRB, before implementation of substantial changes. Relevant safety information will be submitted to the IEC during the course of the trial in accordance with national regulations and requirements.

Initial IEC positive vote, and all materials approved by the IEC for this study including the patient consent form and recruitment materials must be maintained by the Investigator and made available for inspection.

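### As written, the antiemetic note in Table 10 reaches Grade 4 vomiting, for which the row above it recommends stopping treatment for good

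*Combined protocol and SAP*

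**What the plan says.** Table 10 in Section 7.2.1 of the protocol has three nausea/vomiting rows and a note beneath them.

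- Grade 1-2: both drugs continue at the current dose, with antiemetics.
- Grade 3: both drugs are withheld for up to 4 weeks and resumed on recovery to Grade 0 or 1.
- Grade 4: "Encorafenib and/or binimetinib should be permanently discontinued". The row sets no condition about response to antiemetics.
- Note: dosing is interrupted for vomiting of Grade 3 or above (written with a ≥ sign), or for Grade 3 nausea (no such sign), "only if the vomiting or nausea cannot be controlled with optimal antiemetics".

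Other text bears on how these lines are read.

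- The title of Table 10 describes its content as "Recommended dose modifications associated with treatment-related adverse events".
- Section 7.2 ties every dose modification to the worst CTCAE grade reached beforehand.
- Section 7.2.1 bases reduction, interruption and discontinuation decisions, all three named, on CTCAE grade and on the guidelines that follow (its pointer is to Table 8).
- Section 7.2.2 sets follow-up for "Patients whose treatment is interrupted or permanently discontinued due to an adverse event", so it treats interruption and permanent discontinuation as separate actions.
- Section 7.2.2.3 states: "Dose interruption/reduction decisions for nausea and/or vomiting should be based on the CTCAE grade of the toxicity", and refers to Table 10. It also says that the treating physician's clinical judgment should guide each patient's management.
- Section 9.3.3 describes Grade 4 as "Life-threatening consequences; urgent intervention indicated".

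**The concern.** One clinical situation is covered by two lines that disagree: Grade 4 vomiting that antiemetics bring under control. The row recommends a permanent stop. The note, taken at its word, does not call even for a temporary hold.

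Two sites could handle the same event in opposite ways. Following the note means renewed exposure after a life-threatening toxicity. Following the row ends study treatment altogether, because Sections 7.1.3 and 7.2.1 stop both drugs once either is permanently stopped. What is at stake is consistent, safe dosing in a rare situation. The efficacy analysis is not involved.

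**Working it through.** No arithmetic applies. The check sets the rows and the note side by side for each situation that the note could reach.

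| Situation | Table 10 row | Note | Compatible? |
|---|---|---|---|
| Grade 3 nausea or vomiting, not controlled | Withhold | Interrupt | Yes |
| Grade 3 nausea or vomiting, controlled | Withhold | Do not interrupt | Yes, if the note qualifies the hold |
| Grade 4 nausea | Stop permanently | Silent (nausea is limited to Grade 3) | Yes |
| Grade 4 vomiting, not controlled | Stop permanently | Interrupt | Both stop dosing; the row goes further |
| Grade 4 vomiting, controlled | Stop permanently | Do not interrupt | No |

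Only the last line conflicts. The next question is whether other text settles it.

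1. Under the worst-grade rule in Section 7.2, later control by antiemetics does not move the event out of the Grade 4 row. This favours the row.
2. Section 7.2.1 ties discontinuation, by name, to CTCAE grade. This also favours the row, but the same sentence defers to the dosing guidelines and ranks no table row above a note.
3. Section 7.2.2 separates interruption from permanent discontinuation. On that footing the note may speak only to temporary holds. This favours the row.
4. Section 7.2.2.3 again points to the grade, but names interruption and reduction only. It sends the reader back to Table 10, where the conflict sits, and adds clinical judgment, which a site could cite either way.

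Four provisions lean towards the row. None states that it prevails.

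Last, the ≥ sign itself. Grade 3 is the only nausea/vomiting row with a hold to qualify. If the note is confined to that hold, the sign governs nothing. The note also uses the sign for vomiting and omits it for nausea in the same sentence, so a careful reader could take the upward reach as deliberate.

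**The case against.** The strongest reply is that the row and the note govern different actions. The note conditions a temporary interruption, the row recommends a permanent stop, and Sections 7.2.1 and 7.2.2 keep the two apart. Nothing in the note says that dosing may continue after Grade 4 vomiting. Together with the worst-grade rule, this makes the row the better reading, and the ≥ sign looks like loose drafting. That much stands. It does not remove the problem, because a site told not to interrupt is unlikely to infer that it should stop for good, and no text gives the row precedence.

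A second reply is that the table is advisory and Section 7.2.2.3 leaves room for clinical judgment. This also stands in part: the protocol does not contain two binding orders in contradiction. But Sections 7.2 and 7.2.2.3 send investigators to Table 10 for the decision, so conflicting advice there still matters.

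A third reply is that an immediately life-threatening event is a serious adverse event, reportable within 24 hours (Sections 9.2.1.2 and 9.4.2), so the sponsor would soon know. True, but that report does not tell the site which line to follow. The practical reach may also be small by now: Section 3.5 of the SAP records 4 patients still on treatment at database closure.

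A reader might go further and infer that the protocol directs sites to keep dosing after life-threatening vomiting. The documents do not support that. The note never says so, and the surrounding rules lean the other way.

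**Conclusion.** The inconsistency is real and narrow. It concerns Grade 4 vomiting controlled by antiemetics, and it arises from reading the ≥ sign literally. The row is the better-supported reading, but the protocol does not say that it prevails, so a site could rely on the note to continue dosing.

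Severity is minor. The point concerns consistency of dosing-safety guidance and has no effect on the primary analysis, alpha or sample size. No number of affected patients can be derived, because the documents give neither a rate of Grade 4 vomiting nor the share that antiemetics control. A reader should not infer from it any bias in the intracranial response rate. The conclusion rests on the wording alone and assumes nothing about how sites have in fact acted.

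**What to change.** Delete the ≥ sign in the note under Nausea/Vomiting in Table 10, so that the note covers Grade 3 only and the Grade 4 row stands unqualified. The sponsor should first confirm that this is the intent. If controlled Grade 4 vomiting was meant to be an exception, the exception belongs in the Grade 4 row instead. Absent such an intent, deletion is the safer default after a life-threatening event and agrees with the grade-based rules in Sections 7.2 and 7.2.1.

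The cost is one character, plus a memo to sites or inclusion in the next amendment. If the sponsor judges the change substantial, Section 11.4 requires ethics committee submission before implementation. Data collection and analysis are unaffected. The small clinical downside is that a patient whose Grade 4 vomiting has been brought under control would stop study treatment.

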# 7.2.2. Follow-up for toxicities

Patients whose treatment is interrupted or permanently discontinued due to an adverse event or clinically significant laboratory value, must be followed up at least once a week (or more frequently if required by institutional practices, or if clinically indicated) for 4 weeks, and subsequently at approximately 4-week intervals, until resolution or stabilization of the event, whichever comes first. Appropriate clinical experts such as an Ophthalmologist, cardiologist or dermatologist should be consulted as deemed necessary. Further guidelines and recommendations for the management of specific study drug Combination induced toxicities are provided in table 10.

